8.3.3 Per Protocol (PP) Population

The Per Protocol population is the subset of the mITT population excluding patients with major protocol deviations which may affect the efficacy evaluation. Patients in the PP population will be analyzed according to the treatment group to which they were randomized.

Major protocol deviations resulting in a patient being excluded from the PP population will include, but may not be limited to, the following:

- Baseline imaging assessment not performed
- Baseline imaging assessment performed >42 days prior to date of randomization (note that although the screening period for baseline imaging assessment was 28 days, an additional 14-day window is being applied so that only baseline imaging assessments >42 days before randomization will be deemed to be a major protocol deviation that may affect the efficacy evaluation)
- Post-randomization imaging assessments not performed for 3 consecutively planned timepoints (i.e. the number of days between imaging assessments is >224 days), defined as
 - the first post-randomization imaging assessment, prior to progression (i.e. prior to date of progression) as assessed by investigator according to RECIST 1.1, occurs at >32 weeks (i.e. >224 days) after randomization, or
 - any post-randomization imaging assessment, prior to progression as assessed by investigator according to RECIST 1.1, occurs at >32 weeks (i.e. >224 days) after the previous post-randomization imaging assessment
- Randomized study treatment not received (TheraSphere and/or sorafenib) prior to progression as assessed by investigator according to RECIST 1.1
- Y90 (including TheraSphere) received by patients in the control arm prior to progression assessed by investigator according to RECIST 1.1
- TheraSphere dose absorbed by perfused volume (as defined in Section 6.5.1.1) lower than the protocol stated range of 120 Gy – 10% (i.e. <108 Gy) prior to progression as assessed by investigator according to RECIST 1.1
- Bilobar disease at baseline (as defined in Section 6.5.1.1) but only one lobe treated with TheraSphere prior to progression assessed by investigator according to RECIST 1.1
- For patients enrolled under all protocol versions implemented:
 - For the control arm:
 - Start of sorafenib >28 days after randomization

- o For the treatment arm:
 - First administration of TheraSphere prior to progression >35 days after randomization, or
 - Start of sorafenib >42 days after the last TheraSphere administration prior to progression

The deviations listed above will be programmatically determined. In addition, monitoring notes or data listings will be reviewed to determine any major deviations that are not identifiable via programming, and to check that those identified via programming are correctly classified. The final classification of major protocol deviations and decisions to exclude patients from the Per Protocol population will be made at the time between the database soft close and hard lock.

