8.3 Analysis Populations

8.3.1 *Modified Intent-to-Treat (mITT) Population*

All randomized patients who met the study eligibility criteria at randomization will form the modified Intent-to-Treat (mITT) Population and will be analyzed according to the treatment group to which they were randomized. This population will be used to analyze all efficacy endpoints.

8.3.2 *Safety Analysis (SA) Population*

All randomized patients who received study treatments at least once, prior to progression (i.e. prior to date of progression) as assessed by investigator according to RECIST 1.1, will form the Safety Population and will be analyzed according to the treatment actually

received prior to progression. Note that patients who received only TheraSphere (no sorafenib) prior to progression do not receive full treatment of either protocol-defined treatment group, so will be analyzed as a separate group in the safety population. This population will be used in all safety reporting and analysis.

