8.6 Analysis of Efficacy Parameters

8.6.1 Analysis of Primary Efficacy Variable

The primary efficacy analysis is of OS. OS rates will be derived from the Kaplan-Meier estimates for each treatment group; 6, 12, 18 and 24 month OS rates will be presented, together with 95% confidence intervals (CIs). Quartiles will be presented and 95% CIs will also be calculated on the quartiles for each treatment group. A log-rank (two-sided) test, converted to a z-score, will be used to compare OS between the two treatment groups at an overall two-sided alpha level of 0.05. The two-sided alpha level of 0.05 will be adjusted over the 2 planned interim analyses and final analysis (as described in Sections 7.4 and 7.5). The HR and corresponding two-sided 95% CI for the treatment effect will be computed from a Cox proportional hazards model. Plots of the Kaplan-Meier curves will be provided for each treatment group. This analysis will be performed on the mITT population (primary analysis) and PP population (secondary analysis).

The assumption of proportional hazards used to compute the HR for OS will be assessed. Firstly, a plot of log[-log (estimated probability of event-free survival)] versus log(time) will be examined, with nonparallel curves for the 2 treatment groups indicating non-proportional hazards. Also, a time-dependent covariate Cox regression model (i.e. adding a treatment group by time interaction) will be fitted and if the time-dependent covariate has two-sided p-value <0.15 piecewise HRs over distinct time periods will be calculated.

For each patient that has not known to have died, OS will be censored at the time of last contact date known to be alive.

Note that any patient who is still on the study and has not withdrawn or died at the data cut-off (DCO) date for the final analysis will have an additional survival contact on the day of DCO or within 2 weeks of DCO date, with Patient Contact/Overall Survival log and/or Confirmation of Death eCRF page to be completed accordingly. If patients are confirmed to be alive or if the death date is after the DCO date these patients will be censored at the date of DCO.

All patients should be followed for OS, however, if a patient has not known to have died and not been followed for OS for any reason (i.e. no contact date known alive on Patient Contact/Overall Survival log eCRF page), censoring date will be defined as the latest among the following dates recorded on the eCRF:

- Adverse event start and end dates

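### The Per Protocol set makes TheraSphere patients survive progression-free for longer than control patients to qualify, so its supportive survival result leans toward TheraSphere even with no effect

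*SAP*

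**What the plan says.** SAP 8.3.3 lists the deviations that remove a patient from the Per Protocol set. Both arms share one rule: "Randomized study treatment not received (TheraSphere and/or sorafenib) prior to progression", with progression judged by the investigator under RECIST 1.1. SAP 5.2.5 repeats that such patients are excluded. SAP 8.3.2 shows that the TheraSphere arm needs both components, since "patients who received only TheraSphere (no sorafenib) prior to progression do not receive full treatment of either protocol-defined treatment group".

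The timing rules then differ by arm:

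- Control patients are excluded for "Start of sorafenib >28 days after randomization".
- TheraSphere patients are excluded for "First administration of TheraSphere prior to progression >35 days after randomization" or for "Start of sorafenib >42 days after the last TheraSphere administration prior to progression".
- A TheraSphere patient with bilobar disease at baseline is also excluded if both lobes were due "but only one lobe treated with TheraSphere prior to progression assessed by investigator according to RECIST 1.1".

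OS runs from randomization to death from any cause (SAP 6.4.1). On the OS comparison, SAP 8.6.1 states: "This analysis will be performed on the mITT population (primary analysis) and PP population (secondary analysis". The Per Protocol set is also used for TTP, TTUP, TTSP, time to deterioration in quality of life, and the additional endpoints (SAP 8.6.2, 8.6.3, 8.6.6). The SAP gives no landmark, delayed entry or other correction. The only effect of the exclusions that SAP 7.6 mentions is lower variability.

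**The concern.** Membership of the Per Protocol set depends on events after randomization, and the two arms must wait different lengths of time to satisfy it. A TheraSphere patient who dies or progresses in week 9, before sorafenib, is removed together with that early death or poor prognosis. A similar control patient who started sorafenib in week 2 stays in and is counted. Because the survival clock starts at randomization, the TheraSphere arm is credited with a longer stretch in which, by construction, nobody in the set can die.

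Progression can hardly remove a control patient before day 28: scans come every 8 weeks, and SAP 6.4 disregards those in the first 6 weeks. In the TheraSphere arm the week-8 scan can fall before sorafenib starts. SAP 5.2.5 notes that some patients received part of their randomized treatment only after progression, so the situation does occur in this trial.

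At stake is the reading of the named secondary analysis of the primary endpoint. A favourable Per Protocol hazard ratio beside a null or borderline mITT result could come from the set definition alone.

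**Working it through.** **Windows.**

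- Control: 28 days (week 4).
- TheraSphere, unilobar: 35 + 42 = 77 days (week 11).
- TheraSphere, bilobar: 35 + 28 + 42 = 105 days (week 15), using the 28-day interval that the protocol synopsis calls typical. If the second lobe is treated by day 56 (weeks 5-8, Protocol 9.2.15.1): 56 + 42 = 98 days (week 14).

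SAP 8.3.3 sets no date limit for the second lobe, so neither bilobar sum is a hard cap.

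**Plan's own figures first.** With rho = 1.5 spending at 188, 250 and 417 deaths (SAP 7.4), the recomputed boundaries are 2.429, 2.431 and 2.093 (two-sided p 0.0151, 0.0151, 0.0363). Power with 417 deaths is 80.0% at medians 10.7 v 14.2 months and 79.8% at HR 0.754. These agree with the SAP.

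**What each window removes.** With exponential times and m = days/30.4375, survival is 0.5^(m/10.7) (control median, SAP 4.4). Freedom from progression is 0.5^(m/5.5) (sorafenib TTP median, Protocol 5.3).

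| Day | Alive | Progression-free (TTP alone) |
|---|---|---|
| 28 | 94% | 89% |
| 77 | 85% | 73% |
| 98 | 81% | 67% |
| 105 | 80% | 65% |

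**Null simulation.** There were 3000 trials per scenario, with 468 patients (the effective size in SAP Appendix 5) randomized 1:1 over 60 months and cut off at 417 deaths. Median OS was 10.7 and median TTP 5.5 months in both arms. Progression was dated at 8-weekly scans. Control patients started sorafenib between day 1 and day 28. A patient was kept only if alive and without documented progression at sorafenib start. The log-rank test ran from randomization, and z beyond 1.96 in favour of TheraSphere counted as a false positive (nominal 2.5%).

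The following are assumptions, not document figures: bilobar share, actual start dates, and a TTP-OS correlation from 0 to 0.7. Ranges run across that correlation.

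| Scenario | Null HR | False positives for TheraSphere | TheraSphere patients excluded |
|---|---|---|---|
| Unilobar, fast (sorafenib by day 42) | 0.96 | 5-6% | about 6% |
| Unilobar, typical | 0.92 to 0.90 | 10-17% | 13-15% |
| Half bilobar, typical | 0.90 to 0.84 | 18-37% | 20-24% |
| All bilobar, typical | 0.87 to 0.78 | 25-67% | 26-33% |
| Unilobar, latest (day 77) | 0.87 to 0.78 | 25-64% | 26-33% |
| Bilobar, latest (day 105) | 0.82 to 0.75 | 46-78% | 29-36% |

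Typical means first TheraSphere on day 14-28, second lobe 28 days later, and sorafenib 14-42 days after the last TheraSphere. About 3% of control patients were excluded throughout. False positives favouring control never exceeded 1.2%. The direction holds at zero correlation, where having to survive to sorafenib is enough. A separate null simulation gave HR 0.83 to 0.89 and 18% to 41% for half bilobar disease, and HR 0.95 and 7% for fast unilobar treatment.

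**Checks (correlation 0.5, half bilobar).** All randomized patients: HR 1.00, false positives 2.6% in each direction. Alive and progression-free at day 105 in both arms: HR 1.00, 2.9% for TheraSphere and 2.7% for control, with about 32% of each arm dropped. The bias therefore comes from the unequal qualifying times.

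**The case against.** The strongest reply is that little rests on this analysis. The mITT comparison by randomized arm is primary, error control is stated for that test and the hierarchy of secondary endpoints (SAP 7.5, 8.6.2), and no success rule uses a Per Protocol result. Any per protocol set for a two-step regimen conditions on receiving both steps. This stands, and it limits the point to interpretation.

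The size is also open. The simulation lets every control patient who survives to the start date begin sorafenib by day 28. SAP 8.3.3 also removes controls who start late, never start, or receive Y90 before progression, and in an open-label trial those exclusions may be prognostic. Repeating the null (correlation 0.5, half bilobar) with an extra 0, 5, 10 or 15% of controls excluded, correlated 0.5 with poor survival, moved the HR to 0.84, 0.87, 0.90 and 0.93 and false positives to 38, 26, 16 and 10%. The bias shrinks but keeps its direction. Other TheraSphere-arm exclusions, such as low absorbed dose, were not modelled as prognostic and could push the other way.

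The and/or wording is loose, and the SAP does not say how a death before a scheduled sorafenib start is classified. SAP 5.2.5 and 8.3.2 make exclusion the natural reading, although classifications are reviewed before hard lock.

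Two stronger readings are tempting. A reader might infer that the trial's type I error is inflated. It is not, because the mITT test does not use this set. A reader might also infer that every TheraSphere patient must stay progression-free to week 15. That figure is a sum for bilobar patients at late timing, not a limit printed in the SAP.

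**Conclusion.** The point holds for the Per Protocol analyses only. The set definition gives the TheraSphere arm a longer event-free qualifying period, and the OS log-rank test and HR then favour TheraSphere with no true effect. For half bilobar disease at typical timing, the null HR is about 0.83 to 0.90 with 18% to 41% one-sided false positives. The full span is about 0.96 (5% to 7%) for fast unilobar treatment to 0.75 (78%) at the latest timing. The direction was the same in every scenario run. The size is conditional on bilobar share, start dates, TTP-OS correlation and near-complete control retention, none of which the documents give, so no single value should be read as this trial's bias. Only OS was simulated. The same selection operates on the other Per Protocol time-to-event endpoints, but its size there was not computed.

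**What to change.** In SAP 8.6.1 and the other Per Protocol time-to-event sections (8.6.2.1 to 8.6.2.3, 8.6.3.2, and PFS in 8.6.6), report the Per Protocol results descriptively, with HR and confidence interval but no p-value. State that the set definition biases them toward TheraSphere, and that they will not be used as confirmation of the mITT result.

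A common landmark in both arms may be added as a sensitivity analysis, keeping patients alive and free of investigator progression at that day and counting time from it. The SAP should say that it conditions on a progression status that treatment may change, omits all earlier deaths (including any early treatment deaths), and keeps fewer patients. With no OS effect but an assumed TTP HR of 0.58 to 0.70 (correlation 0.5 to 0.7), a day-105 landmark gave HR 1.03 to 1.07, with about 5% to 7% false positives favouring control, and kept about 65% to 74% of patients. Day 105 is also not a true cap on sorafenib start. The landmark is therefore a trade-off and not a replacement.

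The cost is SAP wording plus, if wanted, one extra run. The downside is that the supportive analysis carries less weight.

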Treatment Group (TheraSphere followed by Sorafenib)	
As soon as possible after randomization, hepatic angiography will be performed to assess hepatic vascular anatomy and tumor hypervascularity, followed by a ^{99m}Tc-MAA scan to rule-out gastrointestinal flow or unacceptable lung shunting. Embolization may be performed, if necessary, to close off gastrointestinal flow so that the patient can qualify for treatment with TheraSphere. The lobe with the highest tumor burden should be scheduled for first treatment with TheraSphere.
 
Patients will not be able to receive TheraSphere if the potential radiation dose to the lungs exceeds 30 Gy for a single treatment or cumulative 50 Gy or embolization cannot be performed to effectively block GI blood flow from the hepatic arterial system. If radiation exposure to the lungs exceeds 30 Gy (or 50 Gy cumulative), dose reduction of TheraSphere is permitted (minimum dose allowed is 90 Gy ± 10%).
 
If after consideration of dose reduction, radiation exposure to the lung continues to be greater than 30 Gy (or 50 Gy cumulative), sorafenib treatment will be initiated as soon as possible and ^{99m}Tc-MAA will be repeated after 4 weeks of continuous treatment with sorafenib. If radiation exposure to the lung is less than 30Gy for a single treatment or 50Gy cumulative within a target dose of 90-120 Gy +10% , the patient may commence treatment with TheraSphere. In such instances, sorafenib should be discontinued at least 7 days prior to the administration of TheraSphere and resume sorafenib at least 2 weeks after the administration of TheraSphere. If radiation exposure to the lung is outside of the permitted range, treatment with sorafenib should be continued.
 
In the case where TheraSphere could not be delivered at target dose of 120 Gy ± 10% within 28 days of randomization, these patients will be included in the Treatment Group Intent-to-Treat analysis, but not in the Treatment Group Per-Protocol analysis.
 
TheraSphere Treatment #1: TheraSphere treatment should occur within 28 days of randomization, and prior to the initiation of sorafenib. The number of infusions required to achieve lobar treatment will be determined by the Investigator, based on the hepatic vascular anatomy.
 
Patients will receive 120 Gy ± 10% of TheraSphere to the treated lobe of the liver and may be administered in multiple infusions to address vascular abnormalities.
 
TheraSphere Treatment #2: Patients who have bilobar disease at randomization should have TheraSphere administered to the untreated lobe. If needed, a second angiogram and/or ^{99m}Tc-MAA scan should be performed. Such treatments typically take place 28 days after the treatment to the first lobe.
 
From 2 to 6 weeks following TheraSphere treatment of all treatable liver tumors observed at the time of randomization, patients should initiate standard-of-care sorafenib treatment in accordance with the sorafenib label directions.
 
Re-treatment of the same patient with further cycles of TheraSphere is permitted if a

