9.2.15.1.6 THERASPHERE ADMINISTRATION

TheraSphere will be administered at a dose of $120 \pm 10\%$ Gy to each lobe of the liver administered in one or more lobar administrations on separate days at least 28 days apart.

Patients in the Treatment group who have hepatic progression with hepatic lesions that are still amenable to TheraSphere are eligible for re-treatment with TheraSphere. In these cases, TheraSphere may be administered at the investigator's discretion using lobar infusions on separate treatment days. If such a patient is being treated with sorafenib, sorafenib therapy should be discontinued at least seven (7) days prior through 2 weeks after hours after TheraSphere administration.

TheraSphere should be administered by appropriately trained or designated personnel from the departments of Radiology, Nuclear Medicine, and/or Interventional Radiology.

TheraSphere administration is generally considered to be an outpatient procedure in the United States. It is generally considered to be an inpatient procedure in Europe. The physical location for after-care and

recovery will be determined by individual institutional policies and facility configurations. The location and sequencing of treatment procedure may vary depending on the physical location of the angiography and nuclear medicine suites, the availability of portable gamma cameras, and the clinical judgment of the physician responsible for the treatment plan.

On the day of treatment, an arterial catheter will be placed percutaneously via the femoral or brachial artery under image guidance. The interventional radiologist performs this procedure. The patency of the catheter is maintained by an infusion of normal saline and a coagulation inhibitor (per institutional protocols) administered via a continuous infusion pump. Proper catheter positioning in the selected location in the hepatic artery will be verified on angiography before TheraSphere administration.

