- TheraSphere dose delivered to lungs prior to progression and post progression

TheraSphere dose absorbed by perfused volume will be calculated as follows.

- Dose absorbed by perfused volume within a lobe (left lobe or right lobe) is defined using data for the corresponding lobe, as the sum of doses delivered by each vial if multiple vials are used to treat same target tissue, or as the weighted average of doses delivered by each vial (weights are target tissue masses) if multiple vials are not used to treat same target tissue.
- Dose absorbed by perfused volume within the liver is defined as the weighted average of doses delivered to each lobe (weights are the sum of target tissue masses in each lobe) for patients who had both lobes treated, and as the single dose delivered for patients who received whole liver dosing.
- Dose absorbed by perfused volume is defined as the dose absorbed by the perfused volume within the treated lobe for patients who had one lobe treated, and dose absorbed by the perfused volume within the liver for patients who had both lobes treated or who received whole liver dosing.

TheraSphere dose delivered to lungs will be calculated as the sum of doses delivered to lungs across all TheraSphere administrations.

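### The Per Protocol dose test averages the two lobes although the protocol sets the dose per lobe, so a patient with one lobe below the limit can stay in the Per Protocol set

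*SAP*

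**What the plan says.** **Protocol.** The dose is stated by lobe. Section 9.2.15.1.6 gives 120 Gy ± 10% as "Gy to each lobe of the liver administered in one or more lobar administrations on separate days at least 28 days apart". The synopsis agrees: "Patients will receive 120 Gy ± 10% of TheraSphere to the treated lobe of the liver". The synopsis also links dose to the PP set. For cases in which the target dose was not achieved in the first 28 days after randomization, it says: "these patients will be included in the Treatment Group Intent-to-Treat analysis, but not in the Treatment Group Per-Protocol analysis".

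**SAP.** Section 8.3.3 lists as a PP exclusion "TheraSphere dose absorbed by perfused volume (as defined in Section 6.5.1.1) lower than the protocol stated range of 120 Gy" minus 10%, which it spells out as below 108 Gy before investigator-assessed progression. Section 6.5.1.1 defines the variable at two levels:

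- A lobe-level dose is derived for the left or right lobe. It is the value tested when only one lobe was treated.
- "Dose absorbed by perfused volume within the liver is defined as the weighted average of doses delivered to each lobe", with target tissue mass as the weight. The value tested is the "dose absorbed by the perfused volume within the liver for patients who had both lobes treated or who received whole liver dosing".

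The only other lobe-specific PP criterion in 8.3.3 excludes bilobar disease with just one lobe treated. SAP 5.2.5 lists departures from the protocol's analysis populations; the move from a per-lobe to an averaged dose is not among them.

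**The concern.** The SAP takes a limit that the protocol defines per lobe and applies it to a mean over two lobes. The discrepancy runs one way. A weighted mean below 108 Gy requires at least one lobe below 108 Gy, but a lobe below 108 Gy does not force the mean below it. So the averaged test never excludes a two-lobe patient whose lobes both reach the limit, and it can keep one whose lobes do not.

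The PP analyses of OS and of the secondary endpoints are meant to describe patients without deviations that affect efficacy evaluation. Under the averaged rule a two-lobe patient with one low lobe can count as treated per protocol, while a one-lobe patient with that same lobar dose is excluded. It also fits poorly with the neighbouring criterion: an untreated second lobe in bilobar disease leads to exclusion, but a second lobe treated well below the limit need not.

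**Working it through.** **1. The plan's own figure.** 120 × (1 − 0.10) = 108 Gy. This reproduces SAP 8.3.3. The upper end of the range is 120 × 1.10 = 132 Gy; the SAP test has no upper limit.

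**2. The rule as written.** Let *w* be the share of target mass in the larger lobe. Then D = *w* × D_large + (1 − *w*) × D_small, and the patient is excluded if D < 108. The documents do not give *w*; I take 0.50 to 0.80 as an assumed range.

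**3. Lowest dose in the smaller lobe that still passes:** (108 − *w* × D_large)/(1 − *w*).

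| *w* | larger lobe 120 Gy | larger lobe 132 Gy |
|---|---|---|
| 0.50 | 96.0 | 84.0 |
| 0.60 | 90.0 | 72.0 |
| 0.65 | 85.7 | 63.4 |
| 0.70 | 80.0 | 52.0 |
| 0.80 | 60.0 | 12.0 |

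These are limits of the rule, not expected doses. If the other lobe is exactly at 108 Gy, any low lobe fails the test.

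**4. Examples at *w* = 0.65 (larger/smaller lobe).**

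- 120/90 Gy: 78.0 + 31.5 = 109.5, kept.
- 100/132 Gy: 65.0 + 46.2 = 111.2, kept. If the larger lobe was treated first, this patient missed the target dose at first treatment, which the synopsis treats as not PP.
- 120/80 Gy: 78.0 + 28.0 = 106.0, excluded.
- 110/90 Gy: 71.5 + 31.5 = 103.0, excluded.

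A per-lobe test would exclude all four.

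**5. How often this could happen.** The documents give no SD, no between-lobe correlation and no mass ratio. Assume Normal lobar doses with mean 120 Gy, a common SD of 8, 12 or 15 Gy, masses 2:1 (*w* = 2/3), and correlation ρ of 0, 0.5 or 0.8.

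- P(mean < 108) = Φ(−12 / (SD × √(*w*² + (1 − *w*)² + 2*w*(1 − *w*)ρ))).
- P(any lobe < 108) at ρ = 0 is 1 − (1 − Φ(−12/SD))²; for ρ > 0 it was simulated.
- Because a mean below 108 implies a lobe below 108, the share kept with a low lobe is the difference between the two.

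At SD 12 and ρ = 0: Φ(−1) = 0.159, so P(any) = 1 − 0.841² = 0.292. The root is √(4/9 + 1/9) = 0.745, so P(mean < 108) = Φ(−1.34) = 0.090. The share kept is 0.292 − 0.090 = 0.202.

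| ρ | kept, SD 8 | kept, SD 12 | kept, SD 15 |
|---|---|---|---|
| 0 | 11% | 20% | 24% |
| 0.5 | 7% | 13% | 15% |
| 0.8 | 4% | 7% | 8% |

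**6. How low the kept lobes are.** With ρ = 0, the share of two-lobe patients kept with a lobe below 81 Gy (90 Gy minus 10%) is 0%, 0.02% and 0.2% at SD 8, 12 and 15. Nearly all kept low lobes are therefore between 81 and 108 Gy.

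**The case against.** **The exclusion list is open and a manual review is planned.** SAP 8.3.3 allows other major deviations to be added and has monitoring notes and data listings reviewed before hard lock. Protocol 15.0 lists a treatment dose outside 90-120 Gy ± 10% as a major deviation, so a very low lobe could be caught there. This stands in part, and it is why such a patient *can* stay rather than *will* stay. It does not close the gap: the review is aimed at deviations that cannot be programmed, a lobar dose can be, and no lobe-level dose rule is written.

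**The protocol has no any-lobe PP rule.** Its PP sentence concerns delivery within 28 days, and the second lobe is scheduled for weeks 5 to 8. This is correct for the second lobe. But the first-treated lobe falls under that sentence, and SAP 8.3.3 itself says it is testing the protocol's range, which is per lobe.

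**A per-lobe rule is stricter on two-lobe patients.** At SD 12 and independence, a one-lobe patient fails with probability 16%; a two-lobe patient fails 9% of the time under the average and 29% per lobe. This is true, and it follows from specifying two doses. It also means patients leave one arm only, on a post-randomization variable, which is a reason to show both versions.

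**A rule for any treated lobe would be too broad.** This stands. SAP 6.5.1.1 has a category of unilobar patients treated in both lobes, and a lobe without disease at baseline should not decide PP membership.

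**Stronger readings that a reader might infer.** One is that every patient with a low lobe is retained; a low lobe that pulls the mean below 108 Gy still leads to exclusion. Another is that grossly under-dosed lobes are commonly kept; step 6 of the working gives at most 0.2% below 81 Gy. A third is that the main trial result is at risk; SAP 8.6.1 makes mITT primary for OS and PP secondary. The documents support none of these.

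**Conclusion.** The mismatch is explicit in the text and does not depend on any assumption: the limit is per lobe in the protocol, and for patients with both lobes treated the SAP tests it on a mass-weighted average. A patient with one lobe below 108 Gy can remain in the PP set.

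The size cannot be computed from the documents. Under the stated assumptions (mean 120 Gy, SD 8 to 15 Gy, 2:1 masses) the share ranges from about 4% of two-lobe patients (correlation 0.8, SD 8) to 24% (independence, SD 15). Some positive correlation is plausible for two lobes of one patient at one site, so the upper figure should not be read as the expected one.

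The effect is confined to the PP analyses of OS and the secondary endpoints. The mITT analysis, the stopping boundaries and Type I error are untouched. It is worth correcting because the PP set does not match the definition the SAP claims for it, and the correction is cheap.

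**What to change.** In SAP 8.3.3, apply the SAP's chosen cut-off to the lobe-level absorbed dose already derived in 6.5.1.1, for each lobe diseased at baseline and treated before progression. Exclude the patient if any such lobe is below the cut-off. Keep the liver-level average for whole-liver dosing and for the exposure summaries. Report the PP results under the averaged rule as a sensitivity analysis, and record the choice in SAP 5.2.5.

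Separately, the 108 Gy limit in SAP 8.3.3 and the 90-120 Gy ± 10% range in Protocol 15.0 must be reconciled. This review does not choose between them.

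**Cost.** The text change is small, and the programming uses a variable that already exists. The treatment-arm PP set becomes smaller: under the assumptions above, by up to the 4-24% of two-lobe patients shown in the working. One limitation remains: within a lobe, vials given to different target tissue are still mass-averaged, so some masking inside a lobe is not removed.
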